As defined in this protocol, “women of childbearing potential” are female patients who are physiologically capable of becoming pregnant.

Conversely, “women of no childbearing potential” are defined as female patients meeting > 1 of the following criteria:

- Surgically sterile (ie, through bilateral salpingectomy, bilateral oophorectomy, or hysterectomy)
- Postmenopausal, defined as:
 - ≥ 55 years of age with no spontaneous menses for ≥ 12 months OR
 - < 55 years of age with no spontaneous menses for ≥ 12 months AND with a postmenopausal follicle-stimulating hormone concentration > 30 IU/mL

APPENDIX 5. NEW YORK HEART ASSOCIATION FUNCTIONAL CLASSIFICATION

Class	Symptoms
I	Cardiac disease, but no symptoms and no limitation in ordinary physical activity, eg, no shortness of breath when walking, climbing stairs etc.
II	Mild symptoms (mild shortness of breath and/or angina) and slight limitation during ordinary activity.
III	Marked limitation in activity due to symptoms, even during less-than-ordinary activity, eg, walking short distances (20-100 m). Comfortable only at rest.
IV	Severe limitations. Experiences symptoms even while at rest. Mostly bedbound patients.

Adapted from Dolgin M, Association NYH, Fox AC, Gorlin R, Levin RI, New York Heart Association. Criteria Committee. Nomenclature and criteria for diagnosis of diseases of the heart and great vessels. 9th ed. Boston, MA: Lippincott Williams and Wilkins; March 1, 1994.

Original source: Criteria Committee, New York Heart Association, Inc. Diseases of the Heart and Blood Vessels. Nomenclature and Criteria for diagnosis, 6th edition Boston, Little, Brown and Co. 1964, p 114.

APPENDIX 6. PROHIBITED MEDICATIONS

Strong and Moderate CYP3A Inhibitors and Strong CYP3A Inducers

Strong CYP3A Inhibitors
Antibiotics: clarithromycin, telithromycin, troleandomycin
Antifungals: itraconazole, ketoconazole, posaconazole, voriconazole
Antivirals: boceprevir, telaprevir
Other: cobicistat, conivaptan, elvitegravir, mibefradil, nefazodone
Protease inhibitors: indinavir, lopinavir, nelfinavir, ritonavir, saquinavir, tipranavir
Strong CYP3A Inducers
Avasimibe, carbamazepine, mitotane, phenobarbital, phenytoin, rifabutin, rifampin (rifampicin), St. John’s wort (Hypericum perforatum)
Moderate CYP3A Inhibitors
Antibiotics: ciprofloxacin, erythromycin
Antifungals: fluconazole
Protease inhibitors: amprenavir, atazanavir, darunavir, fosamprenavir
Calcium channel blockers: diltiazem, verapamil
Tyrosine kinase inhibitors (anticancer): imatinib
Food products: grapefruit and juice (Citrus paradisi), Seville orange and juice (Citrus aurantium)
Herbal medications: Schisandra sphenanthera
Others: aprepitant, casopitant, cimetidine, cyclosporine, dronedarone, tofisopam

Data compiled from the FDA’s “Guidance for Industry, Drug Interaction Studies;” <http://www.fda.gov/drugs/developmentapprovalprocess/developmentresources/druginteractionslabeling/ucm093664.htm> from the Indiana University School of Medicine’s “Clinically Relevant” Table <http://medicine.iupui.edu/flockhart/table.htm>; from the University of Washington’s Drug Interaction Database www.druginteractioninfo.org

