
Concomitant Therapy and Clinical Practice:
 
All treatments and supportive care, including antiemetic therapy, hematopoietic growth factors, and/or red blood cell/platelet transfusions, that the investigator considers necessary for a patient’s welfare may be administered at the discretion of the investigator in keeping with the local standards of medical care. All concomitant medications, including all prescription and over-the-counter drugs, supplements, and intravenous medications and fluids, taken by or administered to the patient within 28 days before randomization and 30 days after the last day of BGB-290 or placebo will be recorded.
 
Patients are not allowed to receive other anticancer therapy, including surgery, radiation therapy, immunotherapy, investigational agents, cytotoxic, biologic or hormone therapy, anticancer Chinese medicine, or herbal remedies ≤ 14 days (or ≤ 5 half-lives, if applicable, whichever is shorter) prior to randomization and during the study. Hormone replacement therapy is allowed. Bisphosphonate and denosumab use is permitted if the patient had already been receiving it at a stable dose > 28 days prior to randomization.
 
The primary metabolic pathway for BGB-290 involves the CYP3A isoform. Administration of strong/moderate inhibitors of CYP3A or strong CYP3A inducers is not allowed. In addition, careful monitoring should be used when co-prescribing CYP2C9 substrates with a narrow therapeutic index, such as phenytoin and warfarin.
	

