- Gastroesophageal reflux disease under treatment with proton pump inhibitors is allowed.
11. Active bleeding disorder, including gastrointestinal bleeding, as evidenced by hematemesis, significant hemoptysis, or melena \leq 6 months before randomization
12. Use \leq 10 days (or \leq 5 half-lives, whichever is shorter) before randomization or anticipated need for food or drugs known to be strong or moderate cytochrome P450 (CYP) 3A inhibitors or strong CYP3A inducers ([Appendix 6](#))
13. Pregnancy or nursing
- a. Females of childbearing potential require a negative serum pregnancy test \leq 7 days before randomization.
14. Significant intercurrent illness that may result in the patient's death before death from gastric cancer
15. Known history of intolerance to the excipients of the BGB-290 capsule

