5.2. Enrollment

After consent has been obtained, each patient will be assigned a unique patient number by the IRT system that cannot be reassigned to any other patient. After determination of eligibility, the investigator will complete the randomization request form and supporting documentation and provide them to the sponsor and/or designee for review and subsequent approval in the IRT system. No eligibility waivers will be granted.

After medical monitor approval, the investigator or delegate will access the IRT system for randomization of the patient based on the protocol-specified stratification factors. The randomization list will be kept by the IRT vendor in their secure system and will not be accessible to the study center, responsible (or designee) monitors, project statisticians, or to the blinded project team at BeiGene, Ltd. (hereafter referred to as BeiGene). Blinded team members will not have access to unblinded information in IRT; this will be managed by clearly defined roles and permissions within the IRT system.

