6.2.2. Prohibited Medications

Patients are not allowed to receive other anticancer therapy, including surgery; radiation therapy; immunotherapy; investigational agents; cytotoxic, biologic, or hormone therapy; anticancer Chinese medicine; or herbal remedies ≤ 14 days (or ≤ 5 half-lives, if applicable, whichever is shorter) prior to randomization and during the study. Hormone replacement therapy is allowed. Bisphosphonate and denosumab use is permitted if the patient had already been receiving it at a stable dose >28 days before randomization.

The primary metabolic pathway for BGB-290 involves the CYP3A isoform. Administration of strong/moderate inhibitors of CYP3A or strong CYP3A inducers is not allowed. Please refer to the drugs/substances listed in [Appendix 6](#) and to <http://medicine.iupui.edu/clinpharm/ddis/main-table/> for a more complete list of medications that are not allowed. Consumption of grapefruit and Seville oranges or their juices are not allowed throughout the study. No other dietary restrictions will apply.

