6.2.3. Medications to Be Used with Caution

Based on preliminary in vitro screening assays, BGB-290 is not a strong inhibitor of other human CYP isoenzymes tested. It is a moderate inhibitor of CYP2C9 ($IC_{50} = 6.48 \mu M$). Investigators need to be aware that BGB-290 has the potential to interfere with the appropriate metabolism of medications that rely on CYP2C9 and follow the prescribing information recommendations for use with CYP2C9 inhibitors. Therefore, careful monitoring should be used when co-prescribing CYP2C9 substrates with a narrow therapeutic index, such as phenytoin and warfarin.

Examples of these medications are listed in [Appendix 7](#) and these should be used cautiously with drug concentration monitoring where appropriate.

In addition to CYP3A, BGB-290 can also be metabolized by CYP2C8 in human liver microsomes, but to a lesser extent. See [Appendix 7](#) for medications that should be used with caution for that reason.

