7.6. Pharmacokinetics

PK samples will be collected from patients at the following time points ([Appendix 1](#)): predose (within 30 minutes before dose) and 2 hours (± 30 minutes) postdose on Cycle 1 Day 1 and Cycle 1 Day 15. The time of study drug administration on the day before Day 15 (Cycle 1 Day 14) must be recorded on the eCRF. Details concerning collection, handling, and processing of the PK plasma samples will be provided in the study manual. PK samples collected from patients assigned to placebo treatment will not be analyzed for BGB-290 concentrations.

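### Phenytoin is prohibited in Appendix 6 but named for monitored use in the synopsis, section 6.2.3 and Appendix 7, so a site could start a banned drug during treatment

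*Protocol*

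**What the plan says.** **Prohibition.** Protocol section 6.2.2 states: "Administration of strong/moderate inhibitors of CYP3A or strong CYP3A inducers is not allowed". It then refers the reader to Appendix 6 for the drugs concerned. Under its strong-inducer heading, that appendix lists "Avasimibe, carbamazepine, mitotane, phenobarbital, phenytoin, rifabutin, rifampin (rifampicin", followed by St. John's wort. Exclusion criterion 12 (section 4.2) applies the same appendix at entry. It covers use shortly before randomization and "anticipated need for food or drugs known to be strong or moderate cytochrome P450 (CYP) 3A inhibitors or strong CYP3A inducers". Section 5.2 adds: "No eligibility waivers will be granted".

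**Caution.** The synopsis (Concomitant Therapy and Clinical Practice) gives the class ban, and its very next sentence reads: "In addition, careful monitoring should be used when co-prescribing CYP2C9 substrates with a narrow therapeutic index, such as phenytoin and warfarin". Section 6.2.3 repeats that advice and says of the Appendix 7 drugs that "these should be used cautiously with drug concentration monitoring where appropriate". Appendix 7 lists phenytoin beside warfarin, footnoted as having a narrow therapeutic index, with no cross-reference to Appendix 6.

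**The concern.** The same drug is banned in one place and offered for monitored use in others, and no sentence ranks the two. An investigator reading only the synopsis or the body text meets phenytoin by name solely as a drug to be monitored, because section 6.2.2 bans the class and leaves the names to the appendix.

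At stake are exposure to study drug and protocol compliance in individual patients. The synopsis and section 6.2.2 identify CYP3A as the main metabolic route of BGB-290, so a strong inducer could lower BGB-290 exposure. A site that followed section 6.2.3 faithfully would also have committed a deviation from the section just before it.

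**Working it through.** No formula applies. The check is to set every place that governs phenytoin side by side.

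| Place in protocol | Names phenytoin? | Instruction |
|---|---|---|
| Synopsis, ban on strong inducers | No (class only) | Not allowed |
| Synopsis, next sentence | Yes | Co-prescribe with monitoring |
| Section 4.2, criterion 12 | No (class, via Appendix 6) | Excluded at entry |
| Section 6.2.2 | No (class, via Appendix 6) | Not allowed |
| Section 6.2.3 | Yes | Co-prescribe with monitoring |
| Appendix 6 | Yes | Prohibited |
| Appendix 7 | Yes | Use with caution |

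1. **Mentions by name.** Appendix 6 prohibits (1). The synopsis, section 6.2.3 and Appendix 7 point to monitored or cautious use (3). Total 1 + 3 = 4.

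2. **Overlap of the two lists.** Appendix 7 contains 4 drugs: celecoxib, phenytoin, warfarin and gemfibrozil. Only phenytoin is also in Appendix 6, so the overlap is 1 of 4. A single overlap looks more like an oversight than a deliberate double listing.

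3. **Precedence.** None of the seven entries says that the ban overrides the caution text, or that the caution text does not apply to phenytoin.

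4. **Direction of the interaction.** Section 6.2.3 rests on BGB-290 inhibiting CYP2C9, and the Appendix 7 footnote is likewise about raised exposure to the substrate. The ban concerns the opposite direction, the effect of an inducer on BGB-290. Checking phenytoin levels does nothing about that.

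5. **When the conflict can arise.** At entry it cannot: criterion 12 cites Appendix 6 alone, and waivers are ruled out. What remains is an unforeseen need arising while the patient is on study drug.

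6. **Whether the consequence would be seen.** Section 7.6 schedules BGB-290 samples predose and 2 hours "postdose on Cycle 1 Day 1 and Cycle 1 Day 15" only. A fall in exposure after a later start would not be measured.

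7. **Effect on the analysis.** The sample size, the 85-event target and the one-sided 0.1 test do not depend on this text. The PFS analysis is by ITT (SAP section 6.4.1), and SAP section 8 drops the Per-Protocol set, so a phenytoin deviation would remove no patient from the PFS analysis.

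**The case against.** The strongest reply is that a reader who applies every rule still arrives at the ban. Section 6.2.2 is explicit and points straight to Appendix 6. In the synopsis, the caution sentence is introduced as an additional restriction, not an exception. A drug can be both a CYP3A inducer and a CYP2C9 substrate, and no sentence says outright that phenytoin is permitted. On this view the count of 1 against 3 records where the name appears and understates the ban, which is stated as a class rule in the synopsis, criterion 12 and section 6.2.2.

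The point about counting is fair: the 1 and 3 are mentions, not operative rules. The stricter reading is also the natural one, but it is not written down, and the wording in section 6.2.3 and Appendix 7 presupposes use.

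The other objections limit the size:

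- **Exposed group.** Brain metastasis and leptomeningeal disease are excluded at entry (exclusion criterion 7). Brain metastases found on study count as progression (Appendix 2), which ends treatment. An obvious route to a new anticonvulsant would therefore normally stop study drug as well.
- **Clinical effect.** The documents give no figure for the effect of phenytoin on BGB-290. Section 1.4.2.1 describes an apparently flat exposure-response for PAR inhibition. Section 1.6 reports maximal target modulation in blood cells at 10 mg against the 60 mg BID study dose, and Table 2 allows reduction to 20 mg BID. A moderate loss of exposure might matter little. The sponsor still chose to prohibit the class.
- **Visibility.** Sparse PK sampling would miss a late change in exposure from any cause, and PK is exploratory. Concomitant medications are recorded until 30 days after the last dose (section 6.2.1), so phenytoin use itself would be visible even though its effect on BGB-290 would not.

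All three stand as limits on the consequence. None removes the contradiction.

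**Conclusion.** The concern holds. The protocol prohibits phenytoin through section 6.2.2 and Appendix 6, presents it as usable with monitoring in the synopsis, section 6.2.3 and Appendix 7, and does not say which governs.

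The consequence is small: few patients, if any, with no number available from the documents, and confined to phenytoin started during treatment. That exposure would fall in such a patient is an inference from the protocol's own account of BGB-290 metabolism and its own ban on inducers; the size of any fall is unknown. Eligibility, alpha, power and the ITT analysis of PFS are not affected.

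It should still be corrected, because it is an instruction to sites that is wrong as written. It also remains relevant after the final analysis, since section 3.1 provides for patients who received BGB-290 to keep receiving it on this study or by another route.

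**What to change.** Delete phenytoin from the synopsis example, section 6.2.3 and Appendix 7. Leave warfarin, celecoxib and gemfibrozil as they are.

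Alternatively, add one sentence to section 6.2.3 and Appendix 7 stating that Appendix 6 prevails for any drug on both lists. This has the advantage of covering any later overlap.

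The cost is close to zero: three deletions or one added sentence, issued in a clarification letter to sites or with the next amendment. No change to the SAP is needed.

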APPENDIX 7. MEDICATIONS TO BE USED WITH CAUTION

Sensitive CYP2C9 Substrates or CYP2C9 Substrates with Narrow Therapeutic Index

- Celecoxib^a
- Phenytoin^b
- Warfarin^b

^a Sensitive substrates: Drugs that exhibit an AUC ratio (AUC_i/AUC) of 5-fold or more when coadministered with a known potent inhibitor, where AUC_i is the AUC of the substrate when coadministered with a known potent inhibitor and AUC is the AUC of substrate alone.

^b Substrates with narrow therapeutic index: Drugs whose exposure-response indicates that increases in their exposure levels by the concomitant use of potent inhibitors may lead to serious safety concerns (eg, Torsade de Pointes).

Strong CYP2C8 Inhibitors

- Gemfibrozil

APPENDIX 8. EUROPEAN QUALITY OF LIFE 5-DIMENSIONS 5-LEVELS HEALTH QUESTIONNAIRE

Under each heading, please tick the ONE box that best describes your health TODAY.

MOBILITY

- I have no problems in walking about
- I have slight problems in walking about
- I have moderate problems in walking about
- I have severe problems in walking about
- I am unable to walk about

SELF-CARE

- I have no problems washing or dressing myself
- I have slight problems washing or dressing myself
- I have moderate problems washing or dressing myself
- I have severe problems washing or dressing myself
- I am unable to wash or dress myself

USUAL ACTIVITIES (e.g. work, study, housework, family or leisure activities)

- I have no problems doing my usual activities
- I have slight problems doing my usual activities
- I have moderate problems doing my usual activities
- I have severe problems doing my usual activities
- I am unable to do my usual activities

PAIN / DISCOMFORT

[figure not shown]
- I have no pain or discomfort
- I have slight pain or discomfort
- I have moderate pain or discomfort
- I have severe pain or discomfort
- I have extreme pain or discomfort

ANXIETY / DEPRESSION

- I am not anxious or depressed
- I am slightly anxious or depressed
- I am moderately anxious or depressed
- I am severely anxious or depressed
- I am extremely anxious or depressed

- We would like to know how good or bad your health is TODAY.
- This scale is numbered from 0 to 100.
- 100 means the best health you can imagine.
0 means the worst health you can imagine.
- Mark an X on the scale to indicate how your health is TODAY.
- Now, please write the number you marked on the scale in the box below.

YOUR HEALTH TODAY =

APPENDIX 10. EUROPEAN ORGANISATION FOR RESEARCH AND TREATMENT OF
 CANCER QUALITY OF LIFE GASTRIC CANCER MODULE QLQ-ST022

EORTC QLQ – ST022

Patients sometimes report that they have the following symptoms or problems. Please indicate the extent to which you have experienced these symptoms or problems during the past week. Please answer by circling the number that best applies to you.

During the past week:	Not at All	A Little	Quite a Bit	Very Much
31. Have you had problems eating solid foods?	1	2	3	4
32. Have you had problems eating liquidised or soft foods?	1	2	3	4
33. Have you had problems drinking liquids?	1	2	3	4
34. Have you had discomfort when eating?	1	2	3	4
35. Have you had pain in your stomach area?	1	2	3	4
36. Have you had discomfort in your stomach area?	1	2	3	4
37. Did you have a bloated feeling in your abdomen?	1	2	3	4
38. Have you had trouble with acid or bile coming into your mouth?	1	2	3	4
39. Have you had acid indigestion or heartburn?	1	2	3	4
40. Have you had trouble with belching?	1	2	3	4
41. Have you felt full up too quickly after beginning to eat?	1	2	3	4
42. Have you had trouble enjoying your meals?	1	2	3	4
43. Has it taken you a long time to complete your meals?	1	2	3	4
44. Have you had a dry mouth?	1	2	3	4
45. Did food and drink taste different from usual?	1	2	3	4
46. Have you had trouble with eating in front of other people?	1	2	3	4
47. Have you been thinking about your illness?	1	2	3	4
48. Have you worried about your weight being too low?	1	2	3	4
49. Have you felt physically less attractive as a result of your disease or treatment?	1	2	3	4
50. Have you worried about your health in the future?	1	2	3	4
51. Have you lost any hair?	1	2	3	4
52. Answer this question only if you lost any hair: If so, were you upset by the loss of your hair?	1	2	3	4

ENGLISH

© QLQ-ST022 Copyright 1999 EORTC Group on Quality of life. All rights reserved.

**APPENDIX 11. CHRONIC KIDNEY DISEASE EPIDEMIOLOGY COLLABORATION
(CKD-EPI) EQUATION**

In adults, the most widely-used equations for estimating glomerular filtration rate (GFR) from serum creatinine are the Chronic Kidney Disease Epidemiology Collaboration (CKD-EPI) equation¹ and the Modification of Diet in Renal Disease (MDRD) Study equation. The National Kidney Disease Education Program (NKDEP) calculators rely on creatinine determinations which are isotope dilution mass spectrometry (IDMS) traceable. All laboratories should be using creatinine methods calibrated to be IDMS traceable. Read more about creatinine standardization.

This CKD-EPI equation calculator should be used when Scr reported in mg/dL. This equation is recommended when eGFR values above 60 mL/min/1.73 m² are desired.

$$\text{GFR} = 141 \times \min(\text{Scr} / \kappa, 1)^\alpha \times \max(\text{Scr} / \kappa, 1)^{-1.209} \times 0.993^{\text{Age}} \times 1.018 [\text{if female}] \times 1.159 [\text{if black}]$$

where:

Scr is serum creatinine in mg/dL,

κ is 0.7 for females and 0.9 for males,

α is -0.329 for females and -0.411 for males,

min indicates the minimum of Scr / κ or 1, and

max indicates the maximum of Scr / κ or 1.

The equation does not require weight because the results are reported normalized to 1.73 m² body surface area, which is an accepted average adult surface area.

The online calculator for CKD-EPI can be found here: <https://www.niddk.nih.gov/health-information/health-communication-programs/nkdep/lab-evaluation/gfr-calculators/Pages/gfr-calculators.aspx>

EORTC QLQ-C30	European Organisation for Research and Treatment of Cancer Quality of Life Cancer Questionnaire
EORTC QLQ-STO22	European Organisation for Research and Treatment of Cancer Quality of Life gastric cancer module
EOT	end of treatment
EQ-5D-5L	European Quality of Life 5-Dimensions 5-Levels Health Questionnaire
HR	hazard ratio
HRD	homologous recombination deficiency
ITT	Intent-to-Treat
LOH	loss of heterozygosity
MedDRA	Medical Dictionary for Regulatory Activities
NCI-CTCAE	National Cancer Institute-Common Terminology Criteria for Adverse Events
NE	not evaluable
ORR	objective response rate
OS	overall survival
PD	progressive disease
PFS	progression-free survival
PK	pharmacokinetic(s)
PR	partial response
PT	preferred term
QTcB	QT interval corrected for heart rate using Bazett's formula
QTcF	QT interval corrected for heart rate using Fridericia's formula
RECIST	Response Evaluation Criteria in Solid Tumors
ROW	rest of world
SAE	serious adverse event
SD	stable disease
SOC	system organ class
TEAE	treatment-emergent adverse event
TSST	Time from randomization to second subsequent anticancer therapy or death
ULN	upper limit of normal

1 INTRODUCTION

The purpose of this statistical analysis plan (SAP) is to describe the procedures and the statistical methods that will be used to analyze and report results for Protocol BGB-290-303: A Phase 2, Double-blind, Randomized Study of BGB-290 (pamiparib) versus Placebo as Maintenance Therapy in Patients with Inoperable Locally Advanced or Metastatic Gastric Cancer that Responded to Platinum-based First-line Chemotherapy. The focus of this SAP is for the planned final analysis specified in the study protocol.

Reference materials for this statistical plan include the protocol BGB-290-303 (version 1.0, 2020-02-13). If the protocol or case report forms are amended or updated then appropriate adjustments to the SAP may be made if they are related to the planned analyses.

The SAP described hereafter is an *a priori* plan. The SAP will be finalized and approved before database lock for the primary analysis of this study. Statistical programming may occur in a blinded manner as study data accumulate to have analysis programs ready at the time of database lock.

